5.9 Indirect Calorimetry

(Week 0, 1, 2, 4, 8, 12, 16, 20 and 24 weeks)

Preparing for the Test

Participants will be advised to abstain from food and alcohol for 7 hours or greater before the IC measurement. Participants will be advised to avoid stimulants and stressors such as caffeine, nicotine, and tobacco for at least 4 hours prior to the test. Beverages allowed include water, caffeine-free and calorie-free drinks. A standard operating procedure for ECAL indirect calorimetry will be adhered to as attached in Appendix.

Steady State Testing

After measuring their height, weight, and other anthropometric data, the participant will lie supine with head elevated 30 degrees, extended limbs in a silent room. In line with safety measures for current COVID19 pandemic, patients will be asked to sit behind a transportable Perspex screen. Using the screen will prevent large droplet dispersal and protect the staff member and surrounding area. Whilst lying in a physically comfortable position, the participant will be asked to maintain a regular inspiratory pattern, avoid moving and speaking during the test. Participant will be advised to remain rested for at least 10 minutes. The mouthpiece will be held with either hand, and participant will be required to breathe through the mouthpiece, with a single-use nose clip applied over the nostrils. The mouthpiece has a two-way filter and will be single-use only. Upon completion it will be disposed of in the clinical waste bin.

REE will be measured using the ECal Indirect calorimetry (Metabolic Health Solutions, Australia) at participant’s bedside. Gas and volume calibration of the device will be performed before each measurement. A mouthpiece will be used to measure inspired oxygen and expired carbon dioxide for up to 6-10 minutes, with the first 2 minutes of data discarded. REE (kcal/day) is calculated by the ECal device. Patients were considered to have reached a steady-state REE if a minimum of 5 consecutive minutes with less than 10% coefficient of variation in VO₂ and VCO₂ was achieved; otherwise repeat testing was indicated.

Accordingly, one measure would be sufficient to measure the REE. However, if the operator cannot guarantee the stability of the readings, the combination of two or three repetitions would increase the precision of the measurements. In such instances, the average of the two best readings will be utilized. A designated and trained healthcare professional will be responsible to operate and check the accuracy of data collection from IC.

Energy expenditure (EE) information obtained from indirect calorimetry includes resting Energy Expenditure (REE) and respiratory quotient (RQ).

Measures to ensure safety relating to the current COVID-19 pandemic will be introduced as per government guidance at the time of the participant visit. At the time of writing, the following measures will be instigated: social distancing, use of protective face masks, and any appropriate personal protective equipment when social distancing not possible. One-way flow of participants and an assessment of any possible COVID-19 symptoms the day prior to attendance and day of attendance. If there are any symptoms, advice will be provided, and the visit rescheduled for a later date and advised to contact local healthcare service and undertake COVID-19 testing. Temperature will be assessed on arrival and if $\geq 37.8^{\circ}\text{C}$ then the visit will be rescheduled. Medical advice / testing will be performed if applicable.

5.11 Food Intake Assessment

Participants are expected and encouraged to adhere to their prescribed dietary intake as advised by their clinicians throughout the study period.

A food diary for every patient will be provided to assist more accurate measure of food consumption. Diary will include all the meals consumed during any two (2) consecutive weekdays and one (1) weekend day before the visit. The assessment will include energy intake, carbohydrate intake, fat intake, protein intake, and fiber intake. The food diary should

be reviewed with the participant in detail for accuracy and completeness by the clinician or the dietician.

5.12 Physical Activity Level

The International Physical Activity Level questionnaire will be administered **at** four intervals during the study at baseline, week 8, 16 and 24. The hours spent in sleep and light, moderate, and hard activities were multiplied by respective metabolic equivalent tasks (METs), summed and finally expressed as total MET-h/d.

5.13 Quality of Life Assessment

Assessment of Quality of Life will be conducted via the IWQoL-Lite & EQ-5D-5L questionnaires. Participants will be asked to complete these questionnaires at the baseline visit and at the final visit.

6 Data storage and analysis

6.1 Source data

The CRF and study questionnaires are the primary data collection instruments. All data requested on the CRF will be recorded. All missing data will be explained. If the item is not applicable, then N/A will be written. All entries will be printed legibly in black ink. If any entry error has been made, to correct the error, a single line will be drawn through the incorrect entry and the correct data entered above it. All such changes will be initialled and dated. For clarification of illegible or uncertain entries, the clarification will be printed above, and this will be initialled and dated.

A copy of the patient consent form and the information sheet will be placed in the hospital notes of all participants and in the Investigator Site File. A sticker will be placed on the cover of the notes (or inside cover) detailing the study title, contact details of the PI, participant ID and the fact that the notes should not be destroyed. All study visits and adverse events will be recorded in the hospital notes.

The PI and his / her staff must ensure that these documents are pseudonymised. Past medical history within the CRF required for inclusion in the study will be verified by participant hospital notes and/or GP medical history.

6.2 Statistical Analysis

Patient characteristics and clinical data will be analysed using SPSS software and STATS Direct. Normally distributed data will be expressed as mean +/- standard deviation (SD). Categorical variables will be analysed by using Chi-squared testing. Continuous variables between groups will be evaluated with unpaired student's t-test (if normal distribution) or Mann-Whitney U test (if not normally distributed). P values < 0.05 will be considered significant.

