Background: Weight loss is important to improve overall health and reduce risk of obesity-related comorbidities such as diabetes. Most effective weight loss methods require a reduction in calorie intake. Some individuals with obesity find it more difficult to lose weight than others, due to inter-individual variation of resting metabolic rate and physical inactivity. Furthermore, individuals with predisposed genetic propensity to obesity who are deemed to be metabolically 'thrifty', require further structured intensification of lifestyle changes. Resting metabolic rate and respiratory quotient have proven to be effective predictors of weight loss.

Aims: This study aims to investigate whether providing energy expenditure information to patients and clinicians during a standardized multicomponent weight management intervention would influence the outcome of weight loss.

Methods: Participants recruited from the University Hospital Aintree weight management clinics, will be subsequently randomised to receive either 1) standard care (SC) - standard multicomponent weight management intervention (diet, exercise, behaviour modification therapy) or 2) intervention group (ECAL) – SC plus use of energy expenditure information to both clinicians and participants to influence dietary advice provided over a 6-month period. Primary outcome measure is the magnitude of weight loss. 7-day food diary used to establish compliance and MET average physical activity scores will be recorded.

This study will adhere to the principles outlined in the UK Policy Framework for Health and Social Care Research (v3.2 10th October 2017). It will be conducted in compliance with the protocol, the Data Protection Act, and other regulatory requirements as appropriate.

GLOSSARY OF ABBREVIATIONS

AE	Adverse Events
BMI	Body Mass Index
BP	Blood Pressure
BPI-SF	Brief Pain Inventory short form
CRF	Case Report Form
CI	Chief Investigator
DN4	Douleur Neuropathique 4
ECAL	Intervention Group
eGFR	Estimated glomerular filtration rate
EQ-5D	European Quality of Life – 5 Dimensions
FBC	Full blood count
HbA1c	Glycated haemoglobin
HDL	High Density Lipoprotein
HRA	Health Research Authority
IC	Indirect calorimetry
IWQoL-Lite	Impact of Weight on Quality of Life - Lite
KOSC	King's Obesity Staging Criteria
LFT	Liver Function Test
LDL	Low Density Lipoprotein
mTCNS	modified Toronto Clinical Neuropathy score
MT	Meal test
NEFA	Non-Esterified Fatty Acids
OSA	Obstructive sleep apnoea
PI	Principal Investigator

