2.2 Secondary Objectives

1. To establish the acceptability and reproducibility of using indirect calorimetry to measure energy expenditure as compared to use of standard predictive energy equations.
2. To determine whether metabolic parameters of REE or RQ are potential surrogate biomarkers to predict weight loss.

3 Study design

Type of study: Randomized-controlled trial

Primary endpoint

Reduction in body weight from baseline to end-of treatment (24 weeks)

4. Study population

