4.4 Sample size

Previous studies in this population from Aintree LOSS(33) community-based, multidisciplinary weight management programme for patients with severe and complex obesity, demographic data of patients who attended had an average weight loss of 1.29 kg (+/- SD 4.88) and mean BMI of 45.6 (+/- SD 6.8) kg/m². The study will have 80% power to detect additional weight loss of 3 kg between the SC and ECAL group. This difference is taken from cornerstone studies like the Diabetes Prevention Programme, which suggests a weight loss of 3-5% of initial body weight would lead to risk reduction in progression of diabetes. Using a power calculator with SD above, the sample size is 42 patients per group; hence n = 84 patients (primary outcome). Allowing for attrition rate of 20%, the sample size required would be $84 / 0.80 = 105$ patients.

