5.2 Baseline visit & Randomisation

Eligible participants will be able to proceed to the Baseline Visit (Week 0). Weight, blood pressure and pulse rate will be recorded for all patients in line with study SOPs. The patient will also complete questionnaires to provide demographic and medical history details and additional data will be collected. Participants will be counselled about the study visits and provided with a food diary to record their food intake during the week. Participants will each receive support from the dieticians and weight management practitioners and/or clinicians with regards to maintaining reduced calorie intake according to their respective groups. Participants may contact their study team or GP at any time.

Eligible participants will then be randomly assigned to one of two groups in a 1:1 ratio:

- 1) The *control group* (SC) – standard care including diet, exercise and behaviour modification therapy. Energy expenditure information (RMR, RQ) measured from IC will be **withheld** from participants until the final visit. Participants will receive a standard nutritional energy goal based on the Harris-Benedict equation, the standard predictive equation used at Tier 3 weight management service at Aintree University

Hospital. Both participants and the study clinician providing advice and care will be “blinded” to the client and practitioner report until the completion of the final visit (week 24). To maintain the “blinding” of both participant and clinician in the SC group, the IC measurement is performed and an electronic copy of this is stored in the database, without showing the report to the participant or clinician. Upon completion of the final visit, SC group participants will be able to request a copy of the relevant client reports, should they wish to do so.

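### Section 6.2 lets the observed distribution choose between a t-test and Mann-Whitney U for the primary endpoint, although the trial is sized on a 3 kg difference in means

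*Protocol*

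**What the plan says.** The Study Summary states: "Primary outcome measure is the magnitude of weight loss". Section 3 makes this the change in weight from baseline to 24 weeks, a continuous variable.

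Section 4.4 sets the target: "The study will have 80% power to detect additional weight loss of 3 kg between the SC and ECAL group". The SD of 4.88 kg comes from an earlier cohort of the same service, and the section concludes: "Using a power calculator with SD above, the sample size is 42 patients per group". That gives 84 in total, or 105 after 20% attrition.

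Section 6.2 is the only analysis text. Its rule for comparing groups is: "Continuous variables between groups will be evaluated with unpaired student's t-test (if normal distribution) or Mann-Whitney U test (if not normally distributed". It sets significance at P < 0.05. It names no separate primary analysis and gives no criterion for normality: no test, no threshold, and no statement of whether the arms are judged separately or together.

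**The concern.** The primary endpoint is continuous and compared between two groups, so the Section 6.2 rule covers it. The trial is designed to detect a difference in kilograms between two means. Under the rule, whether that difference or a rank comparison is tested depends on how the weight changes turn out to be distributed.

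The two tests answer the same question only if one arm's distribution is the other's moved along the scale. A feedback intervention could instead change the shape, for example if some participants respond strongly and others not at all. Mann-Whitney then no longer targets the mean difference. A trial could miss a real 3 kg mean benefit for that reason, or report significance when mean weight loss is the same in both arms. With no stated criterion for normality, the choice is also open to discretion.

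**Working it through.** **1. The plan's own figure.** Inputs from Sections 4.4 and 6.2: difference 3 kg, SD 4.88 kg, power 80%, alpha 0.05 (sidedness not stated), allocation 1:1.

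n per group = 2 × [SD × (z₁₋α/₂ + z₁₋β) / Δ]²

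- Two-sided: 2 × [4.88 × (1.960 + 0.842) / 3]² = 41.5, so 42 per group and 84 in total. With attrition, 84 / 0.80 = 105. All three figures are reproduced.
- One-sided: 33 per group, which does not match.
- Exact t calculation: 42.5, so 43 per group; power at 42 is 79.5%. The gap to 42 is immaterial.

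The trial is therefore sized as a two-sided comparison of means. On normal data a rank test would need about 44 to 45 per group (42 or 42.5 divided by 3/π).

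**2. What the rule does to power.** Simulation of 10,000 trials per case, 42 completers per arm, SD 4.88 in each arm, true mean difference 3 kg. Weight loss is counted as positive, so right skew means a long tail of large losses. Skewed arms are shifted gamma distributions with skewness 1.0, 1.41 and 2.0, mirrored for left skew. Mann-Whitney is used when Shapiro-Wilk gives p < 0.05 in either arm. Shapes and trigger are assumptions.

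| Shape of the arms | Rule in 6.2 | t-test always |
|---|---|---|
| Both normal | 80.3% | 80.3% |
| Only ECAL right-skewed | 72.6 / 69.0 / 68.4% | 80.3 / 81.5 / 82.2% |
| Only ECAL left-skewed | 84.6 / 88.9 / 92.0% | 77.9 / 78.1 / 78.1% |
| Both equally skewed | 84.3 / 90.1 / 96.7% | about 80% |

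Applying Shapiro-Wilk to the pooled data instead gives 76.8 / 74.1 / 71.6% (ECAL right-skewed) and 81.5 / 86.2 / 91.0% (ECAL left-skewed). The direction is the same and the departure from the t-test is smaller.

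**3. False positives.**

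- Arms sharing one distribution: the rule rejects in 4.6 to 5.1% of trials.
- Equal means and SDs, one arm skewed: the rule rejects in about 6 to 10%, the t-test in about 5%.

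**4. What is being compared.** The median of all pairwise differences between arms shows what a rank comparison responds to. With a true mean difference of 3.0 kg it is 2.62 / 2.51 / 2.40 kg if ECAL is right-skewed and 3.37 / 3.49 / 3.61 kg if left-skewed. Under a pure shift it is 3 kg. The two tests disagree on significance in 5.7% of trials with normal arms, 11.1 / 13.7 / 15.0% with ECAL right-skewed and 8.2 / 11.3 / 14.2% with ECAL left-skewed.

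**5. Baseline weight as covariate.** Replacing SD by SD × √(1 − r²), with 81 instead of 82 degrees of freedom, changes power at 42 per arm from 79.50% to 79.49% at r = 0, 79.9% at r = 0.1 and 83.1% at r = 0.3. The document does not give r, the correlation of baseline weight with weight change.

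**The case against.** **An unseen SAP may settle this.** Section 6.2 is short and generic, and a primary model is commonly left to an SAP. That disposes of any complaint about what 6.2 omits. It does not dispose of a rule that 6.2 states and that covers the primary endpoint; an SAP that departed from it would leave the two documents in conflict.

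**Choosing the test by normality is ordinary practice and can gain power.** Both are true, and with equally skewed arms the gain is large. But at 42 per arm the t-test held its level in every shape tried, so the switch is not needed for validity. Nor does every uneven response cost power: if half of ECAL gain exactly 6 kg, power is 72.3% for the t-test and 71.9% for the rule.

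**The size rests on assumed shapes.** This stands. The document supplies only a mean and an SD, and the effect can go either way.

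Some stronger readings are tempting but unsupported:

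- *That Mann-Whitney can never test a mean difference.* Under a pure shift it does.
- *That mean weight loss would go unreported if data are not normal.* Section 6.2 says "Normally distributed data will be expressed as mean +/- standard deviation (SD" and does not say that means are withheld otherwise.
- *That the rule inflates type I error in general.* It does so only when the arms differ in shape.
- *That omitting baseline weight as a covariate is an error.* Section 5.2 has it recorded, but an unadjusted comparison is valid.

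**Conclusion.** The point holds in a limited form. As written, 6.2 makes the hypothesis tested on the primary endpoint depend on the observed distribution, while the trial is sized on a mean difference. The mismatch matters only if the two arms differ in shape.

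In the illustrations with one skewed arm, the rule loses up to about 14 points of power (82.2 − 68.4) or gains about as much (92.0 − 78.1), and false positives rise to at most about 10%. With normal arms there is no cost. With equally skewed arms there is a gain of up to about 17 points (96.7 − 80) at a type I error near 5%. These sizes assume 42 completers per arm, equal SDs of 4.88, gamma-type skew and a Shapiro-Wilk trigger. None of the shapes or triggers comes from the document, so they show what could happen and do not forecast this trial.

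That the rule exists and covers the primary endpoint is certain; its effect on this trial is not. It should be changed because the change is nearly free. The 42/84/105 and the t-test itself are sound.

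**What to change.** In Section 6.2, state that the normality-based choice of test does not apply to the primary endpoint. Name one mean-difference analysis for it, reported in kg with a 95% confidence interval at two-sided alpha 0.05.

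Preferably this is a linear model of week-24 weight, or of weight change, on randomised group with baseline weight as covariate. An unadjusted t-test would cure the defect equally well. Mann-Whitney or robust methods (robust standard errors, bootstrap) can stay as sensitivity analyses. If an SAP exists, it should say the same.

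The cost is one or two sentences, with no added patients, visits or data and no change to 84/105. The covariate uses one degree of freedom. The real downside is that the power a rank test would gain is given up if both arms turn out equally skewed.

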6.3 Storage, archiving and destruction of data

Research data will be stored in an anonymous format. Patients will be given a study number which will then be used to link information without identifying individual patient details. All information and test results will be fed into a secure password protected computer on the 3rd floor of the Clinical Sciences Centre, Aintree University Hospital, and all data and results will be coded and securely stored. The Clinical Sciences Centre has secure facilities including locked doors requiring ID access, ID badges, 24-hour security and alarm system.

The study will end once the last participant has completed the last visit and data filed and collected. After the study end personal data will not be retained and will be destroyed by confidential means. Anonymised data will be kept for 10 years in a locked cupboard on the 3rd floor of the Clinical Sciences Centre, University Hospital Aintree and will then be destroyed by confidential means.

7 Adverse Events

7.1 Definitions

Adverse Event (AE): any untoward medical occurrence in a patient or clinical study subject.

Serious Adverse Event (SAE): any untoward and unexpected medical occurrence or effect that:

- Results in death
- Is life-threatening – refers to an event in which the subject was at risk of death at the time of the event; it does not refer to an event which hypothetically might have caused death if it were more severe
- Requires hospitalisation, or prolongation of existing inpatients' hospitalisation
- Results in persistent or significant disability or incapacity

Medical judgement should be exercised in deciding whether an AE is serious in other situations. Important AEs that are not immediately life-threatening or do not result in death or hospitalisation but may jeopardise the subject or may require intervention to prevent one of the other outcomes listed in the definition above, should also be considered serious.

7.2 Reporting Procedures

All adverse events should be reported. Depending on the nature of the event the reporting procedures below should be followed. Any questions concerning adverse event reporting should be directed to the Chief Investigator in the first instance.

7.2.1 Non-Serious AEs

All such events, whether expected or not, should be recorded.

7.2.2 Serious AEs

An SAE form should be completed and faxed to the Chief Investigator within 24 hours. However, relapse and death due to <condition>, and hospitalisations for elective treatment of a pre-existing condition do not need reporting as SAEs.

All SAEs should be reported to the <name of REC> where in the opinion of the Chief Investigator, the event was:

- 'related', i.e. resulted from the administration of any of the research procedures; and
- 'unexpected', i.e. an event that is not listed in the protocol as an expected occurrence

Reports of related and unexpected SAEs should be submitted within 15 days of the Chief Investigator becoming aware of the event, using the NRES SAE form for non-IMP studies. The Chief Investigator must also notify the Sponsor of all SAEs.

Local investigators should report any SAEs as required by their Local Research Ethics Committee, Sponsor and/or Research & Development Office.

Contact details for reporting AEs

Please send SAE forms to:
Research and Development,
Third Floor Clinical Sciences Building,
University Hospital Aintree,
[name],
Liverpool
[name]
[contact]
[contact]

8 Assessment and Follow-up

All participants should currently be registered with a weight management service. Should they require follow up after the study, they will return to their registered weight management service provider for any follow-ups.

9 Regulatory issues

